3.1.4.3 Definition of DLT

All toxicities will be graded using the Common Terminology Criteria for Adverse Events (CTCAE) version 4.03 ([Appendix A](#)).

The occurrence of any of the following toxicities during DLT evaluation period (ie, occurred during the first 2 dosing cycles) will be considered a DLT, if judged by the investigator to be related to talimogene laherparepvec and/or pembrolizumab:

- Grade 4 non-hematologic toxicity
- Grade 3 non-hematologic toxicity lasting > 3 days despite optimal supportive care, except grade 3 fatigue
- Any grade 3 or higher non-hematologic laboratory value if medical intervention is required, leads to hospitalization, or persists for > 1 week. Laboratory values that persist for > 1 week but are deemed not clinically important per both investigator and sponsor will not be considered DLTs
- Either AST or ALT 3x above baseline/upper limit of normal (ULN) (whichever is higher) AND either international normalization ratio (INR) or total bilirubin (TBL) 2x above baseline/ULN (whichever is higher)
- Grade 3 or 4 febrile neutropenia
 - Grade 3 is defined as absolute neutrophil count (ANC) < 1.0 x 10⁹/L with a single temperature of > 38.3°C (101°F) or sustained temperature of ≥ 38°C (100.4°F) for more than 1 hour
 - Grade 4 is defined as ANC < 1.0 x 10⁹/L with a single temperature of > 38.3°C (101°F) or sustained temperature of ≥ 38°C (100.4°F) for more than 1 hour, with life-threatening consequences and urgent intervention indicated
- Grade 4 thrombocytopenia associated with a bleeding event requiring intervention
 - a bleeding event which does not result in hemodynamic instability but requires an elective platelet infusion, or
 - a life-threatening bleeding event which results in urgent intervention and admission to intensive care unit
- Serious herpetic event: Herpetic encephalitis, encephalomyelitis, or disseminated herpetic infection
- Grade 5 toxicity (ie, death)
- Any other intolerable toxicity leading to permanent discontinuation of talimogene laherparepvec and/or pembrolizumab

- Grade 3 or higher adverse events related to talimogene laherparepvec and/or pembrolizumab, that results in a study treatment delay by > 2 weeks

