- 107 Cohort 3 and 4: sum of tumor diameters from injectable lesions is at least 8 cm (or possibly greater if there are lesions with necrotic cores) and must be eligible to receive > 4 mL of talimogene laherparepvec as defined in Section 6.2.1.1
- 108 Eastern Cooperative Oncology Group (ECOG) performance status of 0 or 1 (see Appendix G)
- 109 Life expectancy approximately 5 months or more
- 110 Adequate organ function determined within 10 days prior to enrollment, defined as follows:
- Hematological (without need for transfusion and or growth factor support within 10 days):
 - ANC $\geq 1500/\text{mm}^3$ ($1.5 \times 10^9/\text{L}$)
 - platelet count $\geq 100\,000/\text{mm}^3$ ($100 \times 10^9/\text{L}$)
 - hemoglobin ≥ 9 g/dL (90 g/L)
 - Renal:
 - serum creatinine $\leq 1.5 \times \text{ULN}$, or 24-hour creatinine clearance ≥ 60 mL/min for subject with creatinine levels $> 1.5 \times \text{ULN}$. (Note: Creatinine clearance need not be determined if the baseline serum creatinine is within normal limits. Creatinine clearance should be calculated per institutional standard).

- Hepatic:
 - serum TBL $\leq 1.5 \times$ ULN
 - AST $\leq 5 \times$ ULN
 - ALT $\leq 5 \times$ ULN
 - Alkaline phosphatase (ALP) $\leq 5 \times$ ULN
- Coagulation:
 - Prothrombin time (PT) or INR $\leq 1.5 \times$ ULN partial thromboplastin time (PTT) or activated PTT (aPTT) $\leq 1.5 \times$ ULN

111 Child-Pugh score of A ([Appendix F](#))

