6.2.1.2 Dosage Adjustments, Delays, Rules for Withholding or Restarting, Permanent Discontinuation

Dose concentration reductions of talimogene laherparepvec are not permitted. However, a reduction in the volume injected due to a disease response is permitted.

For subjects that have an INR of > 1.5 or platelet $< 50,000/\text{mm}^3$ ($50 \times 10^9/\text{L}$) prior to injection, talimogene laherparepvec administration should be delayed until INR is ≤ 1.5 or platelet $\geq 50,000/\text{mm}^3$ ($50 \times 10^9/\text{L}$) without transfusion. Any planned correction of INR or platelet count with transfusion prior to injection should be first discussed and approved with the sponsor medical monitor.

If a subject experiences any of the following treatment-related toxicities, talimogene laherparepvec administration should be delayed until the toxicity has resolved to at least CTCAE version 4.03 grade 1:

- grade 2 or greater immune-mediated adverse events, with the exception of vitiligo.
- grade 2 or greater allergic reactions.
- any other grade 3 or greater hematologic toxicity
- any grade 3 or higher non-hematologic laboratory value unless deemed not clinically important per both investigator and sponsor.

For hepatotoxicity stopping rules refer to Section 6.4.

If a subject requires corticosteroid dosing of > 10 mg prednisone daily (or equivalent, eg, 1.5 mg dexamethasone) for any reason, talimogene laherparepvec and pembrolizumab dosing must be held until the corticosteroid dose has decreased to ≤ 10 mg prednisone daily (or equivalent).

All necessary supportive care shall be available to subjects except for those listed in Section 6.9. Talimogene laherparepvec treatment should be continued based on the potential risk/benefit assessment of the subject.

If talimogene laherparepvec treatment was delayed by > 2 weeks, that dose will be deemed to have been missed and the subject will proceed to the next scheduled treatment visit.

If talimogene laherparepvec dosing is delayed by more than 6 weeks from the date of the planned dose (ie, approximately 9 weeks from the previous dose) due to the occurrence of an adverse event that is considered related to talimogene laherparepvec, the subject must be permanently taken off talimogene laherparepvec treatment.

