If talimogene laherparepvec dosing is delayed by more than 6 weeks from the date of the planned dose (ie, approximately 9 weeks from the previous dose) for reasons other than treatment-related toxicity, the case must be reviewed by the Amgen medical monitor in conjunction with the investigator to determine if the subject can resume talimogene laherparepvec therapy.

Talimogene laherparepvec is to be permanently discontinued for subjects meeting any of the following criteria:

- Subject developed a DLT during the DLT evaluation period (please refer to Section 3.1.4.3).

- The subject, for any reason, requires treatment with another anti-cancer therapeutic agent for treatment of the study disease (other than the exceptions noted in Section 6.6). In this case, discontinuation from the treatment occurs immediately upon introduction of the new agent.
- Confirmed PD occurs as defined per modified irRC-RECIST ([Appendix D](#)).
- A grade 2 or greater immune-mediated adverse event (with the exception of vitiligo) or allergic reactions attributed to talimogene laherparepvec that would require a dose delay of greater than 6 weeks from the date of the planned dose (ie, approximately 9 weeks from the previous dose).

NOTE: immune-mediated glomerulonephritis, vasculitis, and pneumonitis and exacerbation of psoriasis have been observed in subjects receiving talimogene laherparepvec in clinical trials. Most of these subjects had a history of other autoimmune disease and/or prior treatment with agents that offered plausible alternative etiologies, however, immune-mediated adverse events can potentially involve any organ system.

- Any other talimogene laherparepvec-related non-hematologic or hematologic toxicities Grade 3 or greater occur that, in the opinion of the investigator, would require a dose delay of greater than 6 weeks from the date of the planned dose (ie, approximately 9 weeks from the previous dose).
- A female subject becomes pregnant or fails to use acceptable method(s) of effective contraception (for those subjects who are able to conceive).
- A female subject breast feeds while on study treatment.
- Concurrent medical illness that, in the judgment of the investigator, would make continued treatment with talimogene laherparepvec dangerous for the subject.

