Dosing should be permanently discontinued if, in the opinion of the investigator, the subject develops clinical evidence of any serious herpes infection (such as HSV hepatitis, encephalitis, or disseminated infection). Systemic anti-herpetic drugs (eg, acyclovir, valacyclovir, or famciclovir) should only be reserved for suspected cases of severe herpetic infection as outlined in the Guidelines for Suspected Serious Herpetic Infections document, but topically administered anti-herpetic drugs may be administered for limited suspected herpetic skin lesions after they are swabbed and tested for talimogene laherparepvec using qPCR.

For Part 1 Group A Cohorts 1-6, Part 1 Group B Cohorts 5 and 6a, and Part 2 Arms I-VI, in subjects with history of HBV and HCV, viral load should be rechecked when ALT or AST are elevated more than twice their baseline value. If reactivation of HBV or HCV is confirmed, discontinuation of talimogene laherparepvec and starting hepatitis antiviral medication should be considered after consultation with the sponsor medical monitor.

For Part 1 Group B Cohort 6b and Part 2 Group B Arm VI subjects with well-controlled viral hepatitis, please see [Table 15](#). Subjects who discontinue talimogene laherparepvec are to continue to return for all other study procedures and

measurements including the 30-day safety follow-up visit (ie, until approximately 30 [+ 7] days after the last dose of study drug) and long term survival follow-up.

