6.4 Hepatotoxicity Stopping and Rechallenge Rules

Subjects with abnormal hepatic laboratory values (ie, ALP, AST, ALT, TBL) and/or INR and/or signs/symptoms of hepatitis (as described in Sections 6.4.1 and 6.4.2) may meet the criteria for withholding or permanent discontinuation of Amgen investigational

product as specified in the Guidance for Industry Drug-Induced Liver Injury: Premarketing Clinical Evaluation, July 2009. Refer to Section 9.2.5.1 for management of hepatic events of clinical interest associated with pembrolizumab.

6.4.1 Criteria for Permanent Discontinuation of Talimogene Laherparepvec Due to Potential Hepatotoxicity

Talimogene laherparepvec should be discontinued permanently and the subject should be followed according to the recommendations in [Appendix E](#) (Drug-induced Liver Injury Reporting and Additional Assessment) for possible drug-induced liver injury (DILI), if ALL of the criteria below are met:

- Current TBL > 2x ULN following baseline TBL < ULN or INR > 1.5
- AND Current AST or ALT > 3x ULN following baseline AST or ALT < ULN, respectively
- AND no other cause for the combination of the above laboratory abnormalities is immediately apparent (ie, dosing should not continue while awaiting the results of pending investigations); important alternative causes for elevated AST/ALT and/or TBL values include, but are not limited to:

Hepatobiliary tract disease

Viral hepatitis (eg, hepatitis A/B/C/D/E, Epstein-Barr Virus, cytomegalovirus, HSV excluding talimogene laherparepvec, varicella, toxoplasmosis, and parvovirus)

Right sided heart failure, hypotension or any cause of hypoxia to the liver causing ischemia

Exposure to hepatotoxic agents/drugs or hepatotoxins, including herbal and dietary supplements, plants and mushrooms

Heritable disorders causing impaired glucuronidation (eg, Gilbert's Syndrome, Crigler-Najjar syndrome) and drugs that inhibit bilirubin glucuronidation (eg, indinavir, atazanavir)

Alpha-one antitrypsin deficiency

Alcoholic hepatitis

Autoimmune hepatitis

Wilson's disease and hemochromatosis

Nonalcoholic fatty liver disease including steatohepatitis (NASH)

Non-hepatic causes (eg, rhabdomyolysis, hemolysis)

Please refer to the Guidelines for Suspected Serious Herpetic Infections for conditions where talimogene laherparepvec may be suspected as a cause of hepatitis and for further management.

6.4.2 Criteria for Conditional Withholding of Talimogene Laherparepvec Due to Potential Hepatotoxicity

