For subjects who do not meet the criteria for permanent discontinuation of talimogene laherparepvec outlined above, talimogene laherparepvec should be withheld if ANY of the following criteria are met, and the subject should be evaluated for DILI:

- Elevation of either AST or ALT according to the following schedule:

Baseline AST or ALT value	AST or ALT elevation
$\leq 3 \times \text{ULN}$	$> 5 \times \text{ULN}$ for ≥ 2 weeks
$\leq 3 \times \text{ULN}$	$> 5 \times \text{ULN}$ and unable to adhere to enhanced monitoring schedule
$\leq 5 \times \text{ULN}$	$> 8 \times \text{ULN}$ at any time

- or: TBL $> 3 \times \text{ULN}$ at any time
- or: ALP $> 8 \times \text{ULN}$ at any time

Talimogene laherparepvec should be withheld pending investigation into alternative causes of DILI. If talimogene laherparepvec is withheld, the subject is to be followed according to recommendations in [Appendix E](#) (Drug-induced Liver Injury Reporting and Additional Assessment) for possible DILI. Re-challenge may be considered if an alternative cause for impaired liver tests (ALT, AST, ALP) and/or elevated TBL, is discovered and the laboratory abnormalities resolve to normal or baseline.

Please refer to the Guidelines for Suspected Serious Herpetic Infections for conditions where talimogene laherparepvec may be suspected as a cause of hepatitis and for further management.

6.4.3 Criteria for Rechallenge of Amgen Investigational Product and Other Protocol-required Therapies After Potential Hepatotoxicity

The decision to re-challenge the subject should be discussed and agreed upon unanimously between the subject and investigator, and between the investigator and Amgen Medical Monitor.

If signs or symptoms recur with re-challenge, then talimogene laherparepvec should be permanently discontinued. Subjects who clearly meet the criteria for permanent discontinuation (as described in Section [6.4.1](#)) should not be re-challenged without consulting the Amgen Medical Monitor.

Pembrolizumab should be permanently discontinued for pembrolizumab-related Grade 3 or 4 increase in AST or ALT with no further rechallenge. If there is another etiology for

the AST or ALT elevation, rechallenge with pembrolizumab may only occur with approval of the medical monitor.

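### The Section 6.4.1 liver stopping rule cannot be met when baseline AST and ALT are both at or above ULN, and Section 6.4.2 has no combined enzyme-plus-bilirubin hold to cover the gap.

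*Protocol*

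**What the plan says.** **Stop (Protocol 6.4.1).** All criteria must hold: TBL above 2x ULN from a baseline below ULN, or INR above 1.5; "Current AST or ALT > 3x ULN following baseline AST or ALT < ULN, respectively"; and no other immediately apparent cause.

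**Eligibility (4.1.1, criterion 110).** Under "Adequate organ function determined within 10 days prior to enrollment, defined as follows", AST, ALT and ALP may each be up to 5x ULN and TBL up to 1.5x ULN.

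**Hold (6.4.2).** For subjects not meeting 6.4.1, "talimogene laherparepvec should be withheld if ANY of the following criteria are met, and the subject should be evaluated for DILI". The limits are:
- AST or ALT above 5x ULN for at least 2 weeks, or without enhanced monitoring (baseline up to 3x)
- AST or ALT above 8x ULN (baseline up to 5x)
- TBL above 3x ULN
- ALP above 8x ULN

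**Dose-limiting toxicity (3.1.4.3).** In the first two cycles, if related, the hepatic limb is "Either AST or ALT 3x above baseline/upper limit of normal (ULN) (whichever is higher"), together with INR or TBL at twice the same kind of reference. Section 6.2.1.2 discontinues T-VEC when "Subject developed a DLT during the DLT evaluation period"; 3.1.4.3 allows case-by-case continuation for clinical benefit.

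**Other T-VEC rules (6.2.1.2).** In any cycle dosing is delayed for INR above 1.5. If treatment-related, it is delayed for "any grade 3 or higher non-hematologic laboratory value unless deemed not clinically important per both investigator and sponsor" and for Grade 2 or higher immune-mediated events. It is held while corticosteroids exceed 10 mg prednisone daily. Two further stops rest on judgment: "Concurrent medical illness that, in the judgment of the investigator, would make continued treatment with talimogene laherparepvec dangerous for the subject", and cases where "the subject develops clinical evidence of any serious herpes infection (such as HSV hepatitis, encephalitis, or disseminated infection").

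**Pembrolizumab rules.** Table 6 withholds pembrolizumab and starts prednisone 0.5 to 1 mg/kg for Grade 2 AST/ALT or bilirubin elevation. Section 6.2.2.3 applies this when the event is judged pembrolizumab-related. Section 9.2.4 requires a 24-hour report in Group A of AST or ALT at least 3x with TBL at least 2x and ALP below 2x ULN. Section 9.2.6 requires study treatment to be held in Group B for listed hepatic events, including TBL above 3.0 mg/dL.

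**The concern.** Concurrent enzyme and bilirubin elevation is the pattern that 6.4.1 is written to catch. Its enzyme criterion counts an enzyme only if it started below ULN, while the eligibility criteria admit subjects for whom neither enzyme did. For them the permanent stop is unreachable. Section 6.4.2 does not fill in, because each of its limits looks at one test alone.

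The DLT definition shows that the protocol already has wording for raised baselines, but that wording is used in the first two cycles only.

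More than the stop is at stake. Appendix E's 24-hour serious adverse event report, repeat liver tests within 24 hours and close observation follow only when Section 6.4 is met. In Part 2 the weekly panels end after week 7. The next scheduled chemistry and coagulation panel then comes before the next injection, 21 (± 3) days on.

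**Working it through.** The question is one of rule logic; the plan states no figure to reproduce. Enzyme and bilirubin values are multiples of ULN.

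**1. Can 6.4.1 be met?** It needs at least one enzyme with baseline < 1 and current value > 3. If baseline AST ≥ 1 and baseline ALT ≥ 1, no current value qualifies, whatever the TBL or INR. Separately, for baseline TBL of 1.0 to 1.5 (also eligible), the bilirubin limb drops out and only INR > 1.5 can satisfy that criterion.

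**2. A worked case.** Inputs: baseline TBL 0.8; current ALT 4.9, TBL 2.9, INR 1.1; AST equal to ALT; ALP under its limit; no other cause apparent. The reworded rule is ALT > 3 × max(baseline, 1) with TBL > 2 × max(baseline, 1). At INR 1.1 this matches the enzyme-plus-bilirubin limb of 3.1.4.3. The combined hold is ALT > 3 and above baseline, with TBL > 2.

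| Baseline ALT | 6.4.1 now | 6.4.2 now | Ratio 4.9 / max(baseline, 1) | Reworded 6.4.1 | Combined hold |
|---|---|---|---|---|---|
| 0.8 | met | no | 4.90 | met | met |
| 1.0 | no | no | 4.90 | met | met |
| 1.2 | no | no | 4.08 | met | met |
| 1.5 | no | no | 3.27 | met | met |
| 1.6 | no | no | 3.06 | met | met |
| 1.67 | no | no | 2.93 | no | met |
| 2.0 | no | no | 2.45 | no | met |
| 3.0 | no | no | 1.63 | no | met |

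Two subjects with identical current values, one with baseline ALT 0.8 and one with 1.2, are treated differently: the first is permanently stopped, while the second meets neither 6.4.1 nor 6.4.2.

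**3. What else acts on these values?**
- INR above 1.5 is delayed by 6.2.1.2, so only INR ≤ 1.5 remains.
- AST/ALT above 5x ULN is Grade 3 on the ULN scale and is delayed if treatment-related, so 3x to 5x remains. (The Table 6 footnotes grade abnormal baselines against baseline. On that scale Grade 3 begins above 5 × 1.2 = 6x ULN at baseline 1.2, and the gap extends higher.)
- TBL above 3x ULN is held by 6.4.2, so above 2x to 3x remains.
- With a normal baseline TBL, bilirubin in that range is Grade 2 in Table 6. If the event is judged pembrolizumab-related, prednisone at 0.5 mg/kg exceeds 10 mg for anyone above 10 / 0.5 = 20 kg, so the steroid rule also holds T-VEC. If it is judged immune-mediated and treatment-related, 6.2.1.2 delays T-VEC directly.

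The gap is therefore AST/ALT above 3x to 5x, TBL above 2x to 3x and INR ≤ 1.5, without either attribution.

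**4. When and where.** The DLT period covers 2 of at most 35 cycles in Part 2: (35 − 2)/35 = 94% lie outside it. In Group B, 3.0 mg/dL is 3.0, 2.73, 2.5 or 2.31x ULN for an assumed ULN of 1.0, 1.1, 1.2 or 1.3 mg/dL, so the hold there narrows the bilirubin range without always closing it.

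**5. Effect of the rewording.** For baselines below ULN, max(baseline, 1) = 1 and the thresholds are unchanged, so no case now caught is lost. The ALT trigger becomes 3.6 at baseline 1.2 and 4.5 at 1.5; it passes 5 at baseline 5/3 = 1.67. The TBL trigger is 2.0 to 3.0 for baseline TBL 1.0 to 1.5. Above baseline ALT 1.67, values up to 5x ULN escape the reworded rule and also escape the DLT rule in cycles 1 and 2.

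**The case against.** A reader might infer that nothing halts T-VEC below the 6.4.2 limits. The documents do not support that. The INR delay has no attribution condition. The Grade 3 laboratory delay applies to treatment-related values. The chain from Table 6 to the steroid hold catches Grade 2 bilirubin or enzyme elevation, with liver tests to be considered weekly or more often. That chain needs attribution, but 6.4.1 has a causality condition too. This objection stands and sets the limits of the gap. What it leaves is the event attributed to T-VEC but not classed as immune-mediated, or left unattributed: precisely the case for which a T-VEC liver rule is needed.

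A reader might also extend the point to Part 1, where 10 of 12 cycles (83%) fall after the DLT period. That does not hold in practice. Part 1 injections go only into liver tumors (6.2.1.1), and those ended with Amendment 6.

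Nor is reporting absent. In Group A the 24-hour event-of-clinical-interest report applies regardless of relatedness or baseline, provided ALP is below 2x ULN. It states no hold, and its follow-up guidance is in a site binder that is not among the documents. A separate herpetic-infection guideline, also not included, may add instructions.

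Finally, rewording a permanent stop could turn some present holds, such as TBL above 3x ULN, into discontinuations. That is a fair cost. Section 6.4.3 softens it by allowing rechallenge after consulting the medical monitor.

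**Conclusion.** The concern holds in this limited form and should be corrected. Section 6.4.1 is unreachable for an eligible group, and the remaining gap is narrow and conditional: the ranges in step 3 of the working, without immune-mediated or pembrolizumab attribution, mainly in Part 2 Group A from cycle 3. The cycle 3 boundary is not absolute, since the DLT rule also misses baselines above 1.67x ULN when current values are at most 5x ULN. Within the gap, a T-VEC stop or hold depends on investigator judgment and the Appendix E steps are not automatic.

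The 94% counts the maximum permitted cycles, not exposure. The documents give no number of subjects with raised baselines or with such elevations, so no expected number of cases can be given. The 5x upper edge assumes grading on the ULN scale, and the Group B range assumes ULN of 1.0 to 1.3 mg/dL. Enrollment has stopped, so only subjects still receiving T-VEC are concerned.

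**What to change.** 1. In 6.4.1, require AST or ALT above 3x the higher of baseline or ULN, with either TBL above 2x the higher of baseline or ULN or INR above 1.5. Keep the criterion on other causes. The enzyme and bilirubin references are those of 3.1.4.3; the INR limit is unchanged.
2. In 6.4.2, add a combined hold: AST or ALT above 3x ULN and above baseline, with TBL above 2x ULN. This reaches baselines above 1.67x ULN, triggers Appendix E and leaves rechallenge open.

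The cost is two criteria reworded and one limit added, with no new data collection. No SAP change is needed, since SAP 9.6.2 already summarizes events of clinical interest. Some further holds, discontinuations and reports will follow, in a number the documents do not allow one to estimate.

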Pneumonitis	Grade 2	Withhold	Administer corticosteroids (initial dose of 1 to 2 mg/kg prednisone or equivalent) followed by taper	Monitor subjects for signs and symptoms of pneumonitis Evaluate subjects with suspected pneumonitis with radiographic imaging and initiate corticosteroid treatment
	Grade 3 or 4, or recurrent Grade 2	Permanently discontinue	Add prophylactic antibiotics for opportunistic infections	
Diarrhea / Colitis	Grade 2 or 3	Withhold	Administer corticosteroids (initial dose of 1 to 2 mg/kg prednisone or equivalent) followed by taper	Monitor subjects for signs and symptoms of enterocolitis (ie, diarrhea, abdominal pain, blood or mucus in stool with or without fever) and of bowel perforation (ie, peritoneal signs and ileus). Subjects with \geq Grade 2 diarrhea suspecting colitis should consider GI consultation and performing endoscopy to rule out colitis.
	Recurrent Grade 3 or Grade 4	Permanently discontinue		Subjects with diarrhea/colitis should be advised to drink liberal quantities of clear fluids. If sufficient oral fluid intake is not feasible, fluid and electrolytes should be substituted via IV infusion.

Footnotes on the last page of the table

Table 6. Dose Modification and Toxicity Management Guidelines for Immune-related Adverse Events Associated With Pembrolizumab

Immune-related AEs	Toxicity grade or conditions (CTCAEv4.03)	Action taken to pembrolizumab	irAE management with corticosteroid and/or other therapies	Monitor and follow-up
AST / ALT elevation or Increased bilirubin	Grade 2 ^a	Withhold	Administer corticosteroids (initial dose of 0.5 to 1 mg/kg prednisone or equivalent) followed by taper	Monitor with liver function tests (consider weekly or more frequently until liver enzyme value returned to baseline or is stable)
	Grade 3 ^b or 4 ^c	Permanently discontinue	Administer corticosteroids (initial dose of 1 to 2 mg/kg prednisone or equivalent) followed by taper	
Type 1 diabetes mellitus (T1DM) or Hyperglycemia	New onset T1DM or Grade 3 or 4 hyperglycemia associated with evidence of β -cell failure	Withhold ^d	Initiate insulin replacement therapy for subjects with T1DM Administer antihyperglycemic in participants with hyperglycemia	Monitor subjects for hyperglycemia or other signs and symptoms of diabetes.
Hypophysitis	Grade 2	Withhold	Administer corticosteroids and initiate hormonal replacements as clinically indicated.	Monitor for signs and symptoms of hypophysitis (including hypopituitarism and adrenal insufficiency)

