Note: Non-irAE will be managed as appropriate, following clinical practice recommendations.

^a AST/ALT: > 3.0 to 5.0 x ULN if baseline normal; > 3.0 to 5.0 x baseline, if baseline abnormal; bilirubin: > 1.5 to 3.0 x ULN if baseline normal; > 1.5 to 3.0 x baseline if baseline abnormal

^b AST/ALT: > 5.0 to 20.0 x ULN, if baseline normal; > 5.0 to 20.0 x baseline, if baseline abnormal; bilirubin: > 3.0 to 10.0 x ULN if baseline normal; > 3.0 to 10.0 x baseline if baseline abnormal

^c AST/ALT: > 20.0 x ULN, if baseline normal; > 20.0 x baseline, if baseline abnormal; bilirubin: > 10.0 x ULN if baseline normal; > 10.0 x baseline if baseline abnormal

^d The decision to withhold or permanently discontinue pembrolizumab is at the discretion of the investigator or treating physician. If control achieved or ≤ Grade 2, pembrolizumab may be resumed.

^e Events that require discontinuation include but are not limited to: encephalitis and other clinically important irAEs (eg, vasculitis and sclerosing cholangitis).

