9.2.6 Events of Clinical Interest for Group B HCC Subjects

Selected nonserious and serious adverse events are also known as ECIs and must be reported to the Sponsor.

Events of clinical interest for HCC subjects in this study include:

1. An overdose of Sponsor's product, as defined in Section 9.2.6.1, that is not associated with clinical symptoms or abnormal laboratory results.
2. Hepatic ECIs include any of the following events if the events are considered not due to disease progression as judged by the investigator. All of these events (if not associated with disease progression under study) will require holding study treatment, notification of the event(s) to the Sponsor within 24 hours after awareness via electronic media or paper.

For dose interval modification, refer to Section 6.2.2.2.1 and 6.2.2.2.2. For guidance related to the diagnosis and management of HECIs, refer to Section 9.2.5.1.

- ALT:
 - a. Among subjects with Baseline ALT < 2 x ULN: ALT ≥ 5 x ULN
 - b. Among subjects with Baseline ALT ≥ 2 x ULN: ALT > 3 x the Baseline level
 - c. ALT > 500 U/L regardless of baseline level
- Total Bilirubin:
 - a. Total bilirubin > 3.0 mg/dL
- Regardless of laboratory values, hepatic decompensation diagnosed clinically, including:
 - New onset clinically detectable ascites requiring intervention for > 3 days
 - Hepatic Encephalopathy
 - Gastrointestinal bleeding suggestive of portal hypertension (e.g., esophageal or gastric varices)

Progression of the cancer under study is not considered an ECI for pembrolizumab unless it is considered to be drug-related by the investigator.

9.2.6.1 Definition of an Overdose of Pembrolizumab for This Protocol and Reporting of Pembrolizumab Overdose

For this trial, an overdose of pembrolizumab will be defined as > 1000 mg (5 times the dose) of pembrolizumab. No specific information is available on the treatment of overdose of pembrolizumab. In the event of overdose, the subject should be observed closely for signs of toxicity. Appropriate supportive treatment should be provided if clinically indicated.

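### For HCC subjects the protocol gives two unreconciled instructions after a pembrolizumab-related Grade 3–4 ALT rise: permanent stop (Section 6.4.3, Table 6) or interruption with restart conditions (Table 15)

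*Protocol*

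**What the plan says.** **Section 6.4.3.** "Pembrolizumab should be permanently discontinued for pembrolizumab-related Grade 3 or 4 increase in AST or ALT with no further rechallenge". The next sentence lets the medical monitor approve rechallenge when another cause explains the rise.

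**Table 6 (Section 6.2.2.2.1).** In the row "AST / ALT elevation or Increased bilirubin", Grade 2 means withhold and Grade 3 or 4 means permanently discontinue. Grades are adjusted for baseline. Grade 3 is "AST/ALT: > 5.0 to 20.0 x ULN, if baseline normal; > 5.0 to 20.0 x baseline, if baseline abnormal" for the enzymes and "bilirubin: > 3.0 to 10.0 x ULN if baseline normal; > 3.0 to 10.0 x baseline if baseline abnormal" for bilirubin. Section 6.2.2.3 applies this guidance to events the investigator attributes to pembrolizumab. There is no Group B exemption.

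**Section 9.2.6.** This defines hepatic events of clinical interest for Group B, provided they are not due to progression. ALT criterion (a) is "Among subjects with Baseline ALT < 2 x ULN: ALT ≥ 5 x ULN". Criterion (b), for a baseline of at least 2 x ULN, is ALT above 3 times baseline. Criterion (c) is ALT above 500 U/L. For bilirubin it is "Total bilirubin > 3.0 mg/dL". Clinical decompensation also counts. AST alone does not.

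**Table 15 (Section 9.2.5.1), immune-related hepatitis row.** A subject enters when any Section 9.2.6 criterion is met and other causes are excluded.
- Both drugs are interrupted for up to 12 weeks and steroids are given.
- Restart requires resolution to Grade 1 or lower or to baseline, a 28-day taper, and prednisone below 10 mg/day.
- Both drugs stop permanently if the laboratory values have not resolved in 3 weeks, if steroids cannot be brought down within 12 weeks, or on Child-Pugh C decompensation.

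**Cross-references.** Section 9.2.6 says "For dose interval modification, refer to Section 6.2.2.2.1 and 6.2.2.2.2", which leads to Table 6, and "For guidance related to the diagnosis and management of HECIs, refer to Section 9.2.5.1", which leads to Table 15. The opening paragraph of Section 6.4 sends pembrolizumab hepatic events of clinical interest to Section 9.2.5.1.

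**The concern.** A site managing an HCC subject with severe immune-related ALT elevation attributed to pembrolizumab can reach either of two instructions. One ends pembrolizumab for good. The other interrupts it and describes how to resume. The pointers do not resolve this. Section 6.4, the hepatotoxicity and rechallenge section, itself leads to Table 15, while Section 9.2.6 leads to both tables. A site that follows Table 15 alone could rechallenge after an injury that Section 6.4.3 treats as a permanent stop.

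At stake is patient safety in people with underlying liver disease. The note in the Table 15 row describes immune-related hepatitis as usually returning on rechallenge.

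**Working it through.** The plan states no figure to reproduce here. The question is whether the two rules cover the same events.

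**ALT.** Let b be baseline ALT in multiples of ULN; inclusion criterion 110 caps it at 5.
- Section 9.2.6 starts at 5 if b < 2 (criterion a), and above 3b if b ≥ 2 (criterion b).
- Table 6 Grade 3 starts above 5 if b ≤ 1, and above 5b if b > 1.

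| Baseline (x ULN) | 9.2.6 starts at (x ULN) | Table 6 Grade 3 above (x ULN) | 9.2.6 event but only Grade 2 |
|---|---|---|---|
| 1 | 5 | 5 | only exactly 5.0 |
| 1.5 | 5 | 5 × 1.5 = 7.5 | 5 to 7.5 |
| 2 | 3 × 2 = 6 | 5 × 2 = 10 | 6 to 10 |
| 3 | 3 × 3 = 9 | 5 × 3 = 15 | 9 to 15 |
| 5 | 3 × 5 = 15 | 5 × 5 = 25 | 15 to 25 |

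For b ≤ 1 the two thresholds coincide at 5. For 1 < b < 2, 5b exceeds 5. For b ≥ 2, 5b exceeds 3b. So every Table 6 Grade 3–4 ALT value is a Section 9.2.6 event, progression aside. A grid check (baseline 0.01 to 5 and on-study ALT 0.1 to 120 x ULN) found 535,024 Grade 3–4 points and none outside Section 9.2.6. Criterion (c) was left out; it can only widen Section 9.2.6.

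**Grading assumption.** Section 6.4.3 does not define its grades; the table uses the baseline-adjusted grades of Table 6. If Section 6.4.3 meant a fixed cut of 5 x ULN at every baseline, then at a baseline of 3 x ULN a rise between 5 and 9 would fall under Section 6.4.3 but not under criterion (b), and the 9 to 15 range would move into conflict. The two rules would still overlap.

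**Bilirubin.** Section 6.4.3 names only AST and ALT, so any overlap is with Table 6. The laboratory ULN is not given. Assume 0.8 to 1.3 mg/dL.
- Normal baseline, Grade 3 above 3 × ULN: 2.4, 2.7, 3.0, 3.6 and 3.9 mg/dL for a ULN of 0.8, 0.9, 1.0, 1.2 and 1.3.
- Baseline at the eligibility cap of 1.5 x ULN, Grade 3 above 3 × 1.5 × ULN: 3.6, 4.05, 4.5, 5.4 and 5.85 mg/dL.

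Against the 3.0 mg/dL trigger the overlap is complete at a ULN of 1.0 or more. Below 1.0 it is partial at a normal baseline.

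**Frequency.** Section 9.2.5.1 gives immune-related hepatitis in about 1–2% of pembrolizumab recipients. For an assumed 20 to 61 combination-treated HCC subjects (61 = design caps 28 + 12 + 21; the actual number is not given), that is 20 × 0.01 = 0.2 to 61 × 0.02 = 1.2 subjects, counting any grade. Section 2.5 reports ALT increased in 8.7% of 23 early combination subjects, printed as grade above 3: 2/23, exact 95% CI 1.1% to 28.0%. That is any cause, both groups together, with intrahepatic injection then in use. Neither figure measures the risk at issue.

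**The case against.** The strongest reply is that nobody is forced to break a rule. Table 15 words its restart items as conditions that must be met, not as a licence to restart, so they can be read on top of the Section 6.4.3 bar. Section 9.2.6 sends dosing questions to Table 6. Table 15 has real brakes, chiefly the permanent stop when values have not resolved within 3 weeks. The protocol also requires treatment to be held, the sponsor to be told within 24 hours, and medical monitor agreement before rechallenge. Finally, Section 6.4.3 bars only pembrolizumab-related rises, so some Grade 3–4 events in the Table 15 row, for instance those attributed to talimogene laherparepvec, could be restarted properly.

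Most of this stands, and it rules out four stronger readings that a reader might infer.
- *The texts cannot both be obeyed.* They can, by applying the stricter one.
- *Table 15 permits rechallenge after any severe liver injury.* Its stop list and restart conditions leave only events that resolve within 3 weeks and meet the steroid conditions.
- *Table 15's restart path is void.* It has a proper role for Grade 2 events at an abnormal baseline and for the row's other triggers.
- *The 0.2–1.2 subjects or the 2/23 give the number at risk.* They are any-grade and any-cause figures.

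The reply does not settle which rule governs. No section directs the reader to add the two rules together. Doing so leaves the ALT-triggered restart path almost empty at a normal baseline. The pointer in Section 6.4 runs to Table 15, which offsets the lean toward Table 6 in Section 9.2.6. The medical monitor works from the same unreconciled text.

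**Conclusion.** The point holds as an unreconciled safety instruction. For a Group B subject with a Grade 3–4 ALT rise that is not due to progression, is judged immune-related and is attributed to pembrolizumab, Section 6.4.3 and Table 6 call for a permanent stop. Table 15 calls for interruption with conditions for resuming. No section sets precedence. The ALT overlap is complete under Table 6's baseline-adjusted grades, assuming Section 6.4.3 uses them. The bilirubin overlap is with Table 6 only and depends on the laboratory ULN.

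The exposed group is small: pembrolizumab-related Grade 3–4 events that resolve within 3 weeks, in HCC subjects still on pembrolizumab now that enrollment has stopped (Section 4). The documents do not allow that number to be estimated. No sample size, power or error rate is affected. It should still be fixed, because the instruction concerns rechallenge after severe liver injury and the repair is brief.

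**What to change.** Add one pembrolizumab-only note to Table 15's immune-related hepatitis row:

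> A Grade 3 or 4 AST, ALT or bilirubin elevation (graded per Table 6) judged related to pembrolizumab requires permanent discontinuation of pembrolizumab per Table 6 and Section 6.4.3; the pembrolizumab restart criteria in this row do not apply to such events. All other events in this row, and talimogene laherparepvec, follow this table and Sections 6.4.1–6.4.3.

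Restricting the note to pembrolizumab-related events preserves the medical monitor's discretion in Section 6.4.3 for other causes, and leaves the row's clinical triggers as they are. Grade 3–4 should not go into Table 15's permanent-stop list: that list covers both drugs, so it would also end talimogene laherparepvec, whereas Section 8.3.1 lets a subject stay on one drug when the other stops. The hepatitis B, hepatitis C and other-cause rows need no change.

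If the sponsor intends Table 15 to govern HCC, the alternative is an explicit Group B exception in Section 6.4.3 and Table 6.

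Either route is a sentence or two by clarification letter or amendment, with no new data or visits. The downside of the note is possibly a few more pembrolizumab discontinuations among HCC subjects still on treatment.
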